3.1 Primary research objectives

Evaluation of the effectiveness and safety of ursodeoxycholic acid in blocking the transmission of infectious novel coronaviruses in adult populations

3.2 Secondary research objectives

- 1) To explore the evaluation of the transition to severe disease in the population infected with novel coronavirus;
- 2) To explore the evaluation of the persistence and reduction of symptoms in people infected with novel coronavirus;
- 3) To explore the evaluation of antibodies in a population of healthy volunteers;
- 4) To observe the safety of ursodeoxycholic acid drugs;
- 5) To evaluating the changes of S protein-specific T/B cell immunity before and after BF.7 infection after immunization with Wuhan Strain vaccine.

4 Study design

This is a single-center, open-ended, single-arm clinical study to evaluate the effectiveness of daily ursodeoxycholic acid plus routine protective measures for the prevention of novel coronavirus infection. The target sample size is 130 medical workers and each healthy volunteer will be followed weekly for nucleic acid/antigen testing or disease progression over an 8-week period for new crown infections.

5 Study population

Healthy volunteers for this study were drawn from medical workers who were not infected with novel coronavirus

5.1 Inclusion criteria

Healthy volunteers suitable for enrollment in this study must meet all of the following criteria:

- 1) Age 18 65 years old.
- 2) No restriction on gender.
- 3) Medical-related personnel (working hours >20 hours per week) serving during the COVID-19 outbreak, including physicians, nurses, medical technicians, administrators, and medical students
- 4) COVID-19 nucleic acid test negative within 48 hours
- 5) Sign the informed consent form

5.2 Exclusion Criteria

Anyone who meets any of the following criteria shall not be selected for this studies:

- 1) Exhibit COVID-19 symptoms, including fever, muscle pain, headache, cough, sore throat, and loss of smell and taste
- 2) Previous infection with novel coronavirus within 6 months
- 3) Previous (past 30 days), current or planned (during the study period) use of immunomodulatory-related drugs
- 4) Those with allergy or intolerance to ursodeoxycholic acid, gallbladder or bile duct disease, severe liver failure, or liver function impairment
- 5) Pregnancy and lactation
- 6) Use of drugs with which ursodeoxycholic acid is contraindicated

7) Other reported health conditions that make participation in the study not in the best interest of the individual

5.3 Off study criteria

Volunteers withdrew from the study for any of the following reasons.

- 1) A healthy volunteer's own request to withdraw from the study.
- 2) planned pregnancy or pregnancy during the trial in female healthy volunteers.
- 3) Loss of visit for various reasons.
- 4) The investigator's judgment should discontinue treatment in this protocol.

Healthy volunteers may withdraw their informed consent if they do not wish to continue to participate in the study. If a healthy volunteer decides to withdraw from the study, the investigator must be notified in a timely manner. The reason for withdrawal from the study should be documented, including the date and reason for withdrawal from the study.

5.4 Rejection Criteria

Volunteers were required to be excluded from the study for the following conditions

- 1) Those who are poorly compliant with the requirements of the study and fail to follow the study plan.
- 2) Those who receive prophylactic medications other than this drug during the trial.

6 Drug delivery measures

Drug Name (Specification Formulation).

Ursodeoxycholic acid capsule, 250mg/capsule.

6.1 Drug delivery method/protocol

Take two capsules orally with a meal, once daily

7 Visiting Arrangements

7.1 Screening Period

- Baseline Collection
 - 1) Basic demographic information such as age and sex.
 - 2) Type of neo-coronavirus vaccination and number of vaccinations received.
 - 3) novel coronavirus infection status of family members/personnel living with them.
 - 4) Personnel positions: e.g., physicians, nurses, medical technology, administrative logistics, medical students, etc.

- 5) Working department.
- 6) underlying disease status: e.g. hypertension, diabetes, cardiovascular disease, etc.
- 7) Combined medication use and drug allergy history.
- Routine Inspection:
 - 1) Vital signs (heart rate, respiration, body temperature, etc.
- Retention of serum samples:
- 1) 5mL of blood was collected from healthy volunteers, of which 2mL of whole blood was directly frozen and the rest was extracted from the serum for freezing and storage.
 - 2) Biological sample processing and storage.

Blood samples will be collected according to the follow-up plan, and the processing and storage will be carried out by the Biosample Bank of the Hospital of Blood Diseases, Chinese Academy of Medical Sciences. It will be managed in strict accordance with biosafety law, regulations on human genetic resources management and other relevant regulations.

7.2 Dosing period (4 weeks)

- 1) weekly nucleic acid testing (in lieu of nucleic acid results if positive for self-test antigens)
 - 2) Weekly telephone follow-up for adverse events.
- 3) 5mL of blood is collected from healthy volunteers at the end of dosing or in case of infection during the period, of which 2mL of whole blood is directly frozen and the rest is extracted from the serum for freezing.

7.3 Follow-up period (8 weeks)

1) If a healthy volunteer develops novel coronavirus symptoms during the follow-up period, the volunteer's symptoms will be scored and recorded according to Table 1.

Table 1: New crown symptom assessment form

Symptoms	Rating				
	Slight =1	Medium =2	Serious =3	Score	
Abdominal					
pain					
fatigue					
Cough					
Shortness of					
breath					
Diarrhea					
Muscle pain					
Headaches					
Taste and					
smell disorder					

Other		
Total Score		

- 1) Weekly telephone follow-up of AE status of healthy volunteers.
- 2) Detection of antibodies before and after drug administration.
- 3) Weekly monitoring of nucleic acid/antigen status of new crowns in healthy volunteers during the study period, and testing for nucleic acid at any time during the study period when volunteers develop symptoms of novel coronavirus (in case of positive self-test antigen, this can be substituted for nucleic acid results)./
- 4) Blood will be collected for freezing and storage in case of infection and out of the group.

Table 2: Table of observation items during the visit

	Baseline period	Detection frequency	In case of infection
Demographic Information	√		
Nucleic acid testing	√	Weekly	√
Vital signs	√		
AE Telephone follow-up AE	√	Weekly	
Blood collection for freezing and storage	√	Week 4 and 8	

[figure not shown]

Figure 1: Research flow chart

[figure not shown]

Figure 2: Flow chart of the visit

8 Research indicators

8.1 Primary research indicators

Prevalence of novel coronavirus infection in healthy volunteers receiving 4 weeks of continuous ursodeoxycholic acid plus conventional protection during the study period, the proportion of healthy volunteers infected with novel coronavirus during the study period as a percentage of the study population

8.2 Secondary research indicators

- 1) The proportion of people infected with novel coronavirus who turned severe.
- 2) the number of days that novel coronavirus symptoms such as fever, sore throat, headache, and muscle aches persisted in the population infected with neo-coronary, and the number of days that the nucleic acid/antigen turned negative.
 - 3) The rate of positive serological antibodies in the population of healthy volunteers.
 - 4) The incidence of adverse events.
- 5) The difference of T/B lymphocyte specific response to Wuhan Strain and BF.7 Strain in different volunteers

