Statistical Methods:

SAS 9.4 software was used for statistical analysis of the data in this study, with continuous variables described by mean \pm stan dard deviation (Mean \pm SD) or median, maximum, minimum, and interquartile range (Median, Max, Min, IQR) and categorical variables described by rate or percentage. Comparisons of measurement data were performed by t-test/ANOVA or nonparametric test; comparisons of count data were performed by $\chi 2$ test or Fisher's exact probability test. If not otherwise specified, all tests were performed as two-sided tests with a test level of α =0.05.

2 Research Background

Researchers at the University of Cambridge, UK, and other institutions have found that ursodeoxycholic acid (UDCA) is able to turn off the ACE2 receptor, thereby blocking viral entry into human cells, and since the SARS-CoV from 2003 to the SARS-CoV-2 spectrum in 2019 utilizes ACE2 as the primary invasion receptor, even if subsequent SARS-CoV-2s continue to show new small variants, the drug maintains its effect. The study was published in Nature on December 5, 2022, entitled "FXR inhibition may protect from SARS-CoV-2 infection by reducing ACE2" [1]. Ursodeoxycholic acid (UDCA) was found to downregulate angiotensin-converting enzyme 2 (ACE2) expression by inhibiting the transcription factor FXR, thereby shutting down the entry of neocoronavirus into human cells. Since the drug acts on the host cell and not on the virus itself, it may be able to prevent current neo-coronavirus infections and should also be able to prevent future neo-coronavirus new mutants, as well as infections by other coronaviruses that utilize ACE2. Currently, China is in a period of high prevalence of neo-coronavirus infections, and there is an urgent need for clinical studies on prophylactic drugs

3 Research objectives

The purpose of this study is to evaluate whether ursodeoxycholic acid is an effective prophylactic agent against novel coronavirus (SARS-CoV-2) infection in medical personnel

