11.3 Statistical analysis methods

SAS9.4 software was used for statistical analysis of the data in this study, and all tests were performed by two-sided test with test level α =0.05 if not otherwise specified.

(1) Basic methods

The measurement data were described by mean \pm standard deviation (Mean \pm SD) or median, maximum, minimum, and interquartile range (Median, Max, Min, IQR); the count data were counted as number of cases and described by rate or percentage; the comparison of measurement data was performed by t test or nonparametric test; the comparison of count data was performed by χ^2 test or Fisher's exact probability test.

2 Analysis of primary endpoint indicators

The number and percentage of healthy volunteers with new coronavirus infection were calculated, and 95% exact confidence intervals were calculated using the Clopper-pearson method.

③ Analysis of secondary endpoint indicators

The $\chi 2$ test or Fisher's exact probability test was used to compare the proportion of neo-coronavirus-infected patients in different subgroups who turned to severe disease and the proportion of neo-coronavirus-infected patients without symptoms, and to calculate the confidence interval respectively; the number of days describing the duration of symptoms such as fever and sore throat in infected patients and the number of days to turn negative were calculated; the antibody status of all healthy volunteers and neo-coronavirus-infected patients were described separately.

4 Analysis of safety indicators

The occurrence of adverse events AE and serious adverse events SAE were recorded and described, and the relevance of the events to the study was determined.

(5) Other analyses

Subgroup and stratified analyses were performed on people of different genders, age groups, staff positions, and staff sections to explore the relationship between the levels of different factors and the effects of neo-coronavirus infection.

12 Ethics Review

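### Secondary indicator 5 does not measure the before/after-infection change named in secondary objective 5, and nothing in the protocol establishes that an infection is BF.7

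*Protocol*

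**What the plan says.** **Objective.** Protocol 3.2, item 5, and the abstract set out to evaluate the "changes of S protein-specific T/B cell immunity before and after BF.7 infection after immunization with Wuhan Strain vaccine".

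**Indicator.** Protocol 8.2, item 5, and the abstract give "The difference of T/B lymphocyte specific response to Wuhan Strain and BF.7 Strain in different volunteers".

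**Analysis.** Section 11.3 has a general rule, "the comparison of measurement data was performed by t test or nonparametric test"; the abstract's version is "Comparisons of measurement data were performed by t-test/ANOVA or nonparametric test". The secondary-endpoint paragraph of 11.3 covers severe disease, infection without symptoms, symptom days and days to a negative test. It ends with "the antibody status of all healthy volunteers and neo-coronavirus-infected patients were described separately". The T/B-cell indicator does not appear there.

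**Infection.** Sections 7.2 and 7.3 use weekly nucleic acid testing and let a positive self-test antigen stand in for it. No section provides for sequencing or lineage typing.

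**Blood.** At screening (7.1), "5mL of blood was collected from healthy volunteers, of which 2mL of whole blood was directly frozen", with serum stored from the rest. Section 7.2 adds a sample at the end of dosing or on infection, and 7.3 one on infection and on leaving the study. Table 2 lists baseline and Weeks 4 and 8, with no mark for blood under infection.

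**The concern.** An indicator should be the measured form of its objective. Here the objective is a change over time around an infection, while the indicator contrasts responses to two strains with no reference to time or infection. A team working from 8.2 could report Wuhan and BF.7 responses across all volunteers at any visit, meet the indicator, and leave the objective unanswered.

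If the indicator is read as a comparison between people, it is also open to confounding. Section 7.1 records vaccine type and number of doses, but lists neither vaccination dates nor earlier infection. The exclusion criteria remove only infections within the past 6 months, and Wuhan-strain vaccination is not an inclusion criterion. Infected and uninfected volunteers could therefore differ in ways that the listed data cannot fully adjust for.

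The strain label is a separate matter. A report on immunity after BF.7 infection would make a claim about the infecting lineage that the protocol's procedures never test. A later analysis plan can choose a test statistic, but it cannot supply typing data that were not collected.

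**Working it through.** **1. Objective against indicator**

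| Element | Objective 5 (3.2) | Indicator 5 (8.2) |
|---|---|---|
| Population | Wuhan-strain vaccinees who become infected | Volunteers, no subset |
| Contrast | After infection against before | Response to one strain against the other |
| Time points | Before and after infection | None |
| Measure | Change | Difference, not over time |

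The closing phrase of the indicator has two readings. It may mean a comparison between volunteers, or the two antigen responses measured across the various volunteers. The before/after element is missing under both.

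**2. Can the planned samples supply the change?** Every volunteer gives blood at baseline, before any infection on study. Later samples from the same person follow on infection, at Weeks 4 and 8, and on leaving. A before/after pair is therefore available in principle. Two gaps remain. Sections 7.2 and 7.3 call for a sample on infection, but Table 2 shows none. No interval after infection is stated, so it is unclear whether a sample drawn when infection is detected counts as after.

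**3. Can the label BF.7 be verified?** The only tests named are nucleic acid and antigen, and the only retained material described is blood. No step identifies the lineage.

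**4. How many infected volunteers?** The protocol gives no calculation for indicator 5. Its only one (11.1) is for the primary endpoint: historical rate 0.35, expected rate 0.20, two-sided α = 0.05, power 90%. It reproduces:

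- n = [(1.960·√(0.35·0.65) + 1.282·√(0.20·0.80)) / 0.15]² = 93.1
- with continuity correction, (n/4)·[1 + √(1 + 2/(n·0.15))]² = 99.7, rounded up to the stated 100
- for 20% dropout, 100/0.80 = 125, covered by the planned 130

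Applying the same rates to 100 and 130 volunteers:

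- at 20%: 0.20 × 100 = 20 to 0.20 × 130 = 26 infected
- at 35%: 0.35 × 100 = 35 to 0.35 × 130 = 45.5, so about 45 infected

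These are upper limits for the paired set, since volunteers without recorded Wuhan-strain vaccination or without a usable later sample drop out of it.

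**5. What precision does that give?** By the normal approximation, the 95% half-width for a mean within-person change is 1.96/√n standard deviations of the change:

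- 1.96/√20 = 0.44
- 1.96/√26 = 0.38
- 1.96/√35 = 0.33
- 1.96/√45 = 0.29

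That is adequate for exploratory description and modest for firm inference.

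**The case against.** The best defence is that the indicator is loosely worded rather than wrong. Its grammatical object is a contrast between two antigens, which each volunteer can supply, and its last phrase may simply mean across the volunteers. Repeat samples are planned, vaccine type and dose number are recorded, and the choice of test may sit in an analysis plan that is not shown. The objective is secondary and exploratory.

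Much of this stands, and it rules out several stronger readings that a reader might infer:

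- **That unpaired tests are prescribed.** They are not. Section 11.3 and the abstract name a t test or a nonparametric alternative without saying paired or unpaired, and assign nothing to indicator 5.
- **That the design cannot answer the objective.** The samples in 7.1 to 7.3 and Table 2 allow a within-person comparison around infection. The indicator as worded and the BF.7 label are what fail.
- **That the baseline sample is wasted.** Section 7.3 also plans antibody testing before and after dosing, and 11.3 describes antibody status.
- **That pairing brings a known gain in precision.** With pre/post correlation r, the variance ratio is 1 − r against two equal independent groups. Against 26 infected and 104 uninfected volunteers it is [2(1 − r)/26] / [1/26 + 1/104] = 1.6(1 − r), so pairing is less precise below r = 0.375. The protocol gives no r and fixes no comparator, so no single figure can be claimed. The case for pairing is that it targets the quantity in the objective.

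The defence does not reach the core. Even on the kindest reading the indicator has no time point, infected subset or change, and no procedure identifies the strain.

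**Conclusion.** The point holds in this limited form. Indicator 5, as written in 8.2 and the abstract, does not measure objective 5, and BF.7 infection is an assumed label. The severity is low: one secondary objective is affected, the primary endpoint is not, and the definition can be repaired from planned samples.

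The size is set by the number infected, about 20 to 26 at the 20% rate or 35 to 45 at 35%. This assumes that the protocol's rates apply and that nearly all infected volunteers are vaccinated and sampled. It also assumes that the stored frozen whole blood and serum can support the intended T/B-cell measurements; the protocol names no assay, so this should be confirmed.

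**What to change.** 1. Redefine indicator 5 in 8.2 and the abstract as the within-person change in T- and B-cell response from the baseline sample to one stated post-infection sample, in infected volunteers with recorded Wuhan-strain vaccination. Report it separately for Wuhan and BF.7 antigens.
2. State the post-infection time point, for example the first scheduled Week 4 or Week 8 sample after infection, and record the interval since the first positive test, because it will vary between people.
3. Add a line to 11.3: paired t test or Wilcoxon signed-rank test, with the estimated change and its 95% confidence interval.
4. Show uninfected volunteers' change over the same period as a descriptive reference. Everyone takes the study drug, so this helps to separate change around infection from change over time on study.
5. Call the exposure SARS-CoV-2 infection during the study period in objective and indicator, unless the strain is confirmed.
6. Reconcile the infection-time blood sample between 7.2/7.3 and Table 2.

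The cost is a rewording of one objective and one indicator, one analysis line, one stated sampling time and one table correction. No new samples are needed if a scheduled visit is used. The price is a small analysis set, and strain confirmation, if wanted, would be extra laboratory work.

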8.3 Safety indicators

Observation and recording of various adverse events during administration of ursodeoxycholic acid in healthy volunteers

9 Adverse events and serious adverse events

All adverse events, including abnormal clinical symptoms and vital signs, and abnormalities in laboratory tests from the date of signing the informed consent to the last visit were recorded, and the characteristics of clinical manifestations, severity, time of occurrence, duration, management and prognosis were recorded, and their correlation with the trial drug/therapeutic regimen was determined.

Adverse events were graded and recorded with reference to NCI CTCAE 5.0

9.1 Adverse Events

9.1.1 Definition of Adverse Events

Adverse event: An adverse medical event that occurs after a healthy volunteer participates in a clinical study, not necessarily related to the study treatment, and includes any

new event that occurs or worsens in severity and frequency compared to the baseline situation, including abnormal results of laboratory tests, physical examinations, etc. Adverse events include Severe adverse event (SAE), Adverse event (AE), and abnormal laboratory results.

9.1.2 Adverse event collection and recording

Adverse events from the date of signed informed consent to the last visit were recorded, and the investigator applied concise medical terminology to report all possible treatment-related adverse events.

9.1.3 Criteria for determining the severity of adverse events

Use the National Cancer Institute Common Terminology Criteria for Adverse Events (CTCAE) version 5.0 to document the severity of adverse events on a scale of 1-5

Grading	Criteria
1	Mild; asymptomatic or mild; seen clinically or diagnostically only; no
1	treatment required
2	Moderate; requires lesser, localized or non-invasive treatment; age-
2	appropriate limitation of instrumental activities of daily living*
	Severe or medically significant but not immediately life-threatening;
3	resulting in hospitalization or prolonged hospitalization; disabling; limiting
	personal activities of daily living \triangle
4	Life-threatening; requires urgent treatment
5	AE-related deaths

^{*} Instrumental activities of daily living: refers to cooking, buying clothes, using the telephone, managing money, etc.

 \triangle Personal activities of daily living: refers to bathing, dressing and undressing, eating, toileting, taking medication, etc., and not bedridden.

Note: the distinction between severity and intensity of the adverse event. Severity is used to describe intensity and is not necessarily an SAE. e.g. a headache may be severe in intensity but cannot be included in an SAE unless it meets SAE criteria.

9.1.4 Criteria for judging the relationship between adverse events and study drug therapy

The investigators analyzed the relevance of adverse events to the study drug treatment according to the principle of determining the relevance of adverse events to the study drug

treatment, which was divided into 5 categories, namely "definitely related, probably related, probably unrelated, definitely unrelated, and undetermined", and "definitely related, probably related, probably unrelated, and The adverse reactions were classified as "definitely related, probably related, probably unrelated and undetermined". The investigator must document the adverse reactions using medical terminology.

	Is it reasonable Time relationship	Is it consistent with known Type of adverse reaction	Whether there are other reasons for The possibility of adverse	
	Time relationship	Type of adverse reaction	events	
Definitely related	Yes	Yes	Yes	
Possibly related	Yes	Yes / No	Uncertain	
Possibly unrelated	No	No	Uncertain	
Definitely not related	No	No	Yes	
Unable to judge	Required information for evaluation is not available			

